### 7.3 Demography and baseline characteristics

Demographic and baseline characteristics will be displayed descriptively.

### 7.4 Prior or concomitant medication and diseases

Prior or concomitant medication and diseases will be listed individually by patient and shown descriptively.

### 7.5 Exposition to treatment/Compliance

The frequency of patients having the FAST PV measurement done on day 1 and day 3 will be shown descriptively. Reasons for missing second doses will be listed.

### 7.6 Primary analysis

Safety will be assessed by determination of the absolute and relative frequencies of AEs and SAEs related to VFI. Related AEs and SAEs include all events that are sure, probable and possible related.

Function of the FAST PV measurement will be assessed by determining the plasma stability of the FD003 high molecular weight marker over the 15, 30, and 60 minute blood draws at day 1 and 3 and applying the following criteria:

- The FAST PV measurement is considered as stable, if the mean plasma concentration of FD003 at 30 minutes is not more than 10% lower than the mean plasma concentration at 15 minutes AND if the mean plasma concentration at 60 minutes is not more than 10% lower than the mean plasma concentration at 30 minutes. The frequency of patients with stable FD003 plasma concentration will be analyzed descriptively for day 1 and day 3.
- The absolute and relative frequency of patients which show a decline in the plasma concentration of FD003 of more than 10% from 15 minutes to 30 minutes and separately from 30 minutes to 60 minutes will be determined for day 1 and day 3.

Further, the change (absolute and relative) in plasma concentration of FD003 from 15 to 30 minutes, and from 30 to 60 minutes will be displayed descriptively for day 1 and day 3 separately.

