#### **10.8.1 Assessment of causality**

To assess causality between administration of the investigational product and the Adverse Event the following definitions apply:

- **Sure:** The reaction comprehensively follows the administration of the investigational product in the right timeframe or can be measured in body tissues or fluids or represents a known or expected response to the study medication or disappears after discontinuation or dose reduction and reoccurs after re-exposure.
- **Probable:** The reaction comprehensively follows the application of the investigational product in the right timeframe or represents a known or expected response to the study medication or disappears after discontinuation or dose reduction and cannot be explained by known characteristics of the patient's disease.
- **Possible:** The reaction comprehensively follows the application of the investigational product in the right timeframe or represents a known or expected response to the study medication, but could easily be caused by other factors.
- **Unlikely:** Event or laboratory test abnormality, with a time to drug intake that makes a relationship improbable (but not impossible); disease or other drugs provide plausible explanations
- **Not related:** Adequate Information supporting the assumption that there is no causality
- **Cannot be evaluated:** The causality cannot be determined.

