### **Size Estimation**

We plan to enrol 50 eligible patients. Due to the explorative nature of this phase II study a formal sample size calculation is not possible. However, the sample size of 50 patients is sufficient to guarantee reasonable accuracy with respect to the main objectives of the trial as specified below.

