## 1 Background

### 1.1 Trial objective

This is an investigator-initiated, one-armed phase II clinical trial designed to primarily evaluate the safety and functionality of the FAST PV and measured Glomerular Filtration Rate (mGFR) Technology in Congestive Heart Failure (CHF) patients.

- Safety will be assessed by determination of the absolute and relative frequencies of AEs and SAEs related to Visible fluorescent injectate (VFI).
- Function of the FAST PV measurement will be assessed by determining the plasma stability of the FD003 high molecular weight marker over the 15, 30, and 60 minute blood draws and applying the following criteria:
  - The FAST PV measurement is considered as stable, if the mean plasma concentration of FD003 at 30 minutes is not more than 10% lower than the mean plasma concentration at 15 minutes AND if the mean plasma concentration at 60 minutes is not more than 10% lower than the mean plasma concentration at 30 minutes
  - We will determine the percentage of patients which show a decline in the plasma concentration of FD003 of more than 10% from 15min to 30min and separately from 30 min to 60min. This percentage should be ideally close to 0.

Secondary objectives are the following:

- To evaluate how estimated plasma volume (ePV) and estimated total blood volume (eTBV) assessments on days 1 and 3 (by established measures as Nadler's formula (eTBV), Kaplan-Hakim formula (ePV), Strauss formula (ePV Change)) predict measured PV (mPV; as assessed by FAST methodology) and measured TBV (mTBV; calculated from mPV and measured hematocrit) at these time points.
- To evaluate how a clinical evaluation (including a reasonable subset of the variables age, gender, BMI, hematocrit, edema grade, presence of pulmonary rales, presence of jugular venous congestion, arterial blood pressure, New York Heart Association (NYHA) stage, respiratory rate) on days 1 and 3 predicts mPV and mTBV at these time points.
- To evaluate whether estimated Glomerular Filtration Rate (eGFR) (calculation by the Chronic Kidney Disease Epidemiology Collaboration (CKD-EPI) formula, sMDRD, Cystatin C formula, and Creatinine-Cystatin C formula) on days 1 and 3 provides an accurate estimate of measured GFR (mGFR; assessed by FAST methodology) in heart failure patients undergoing active fluid management.
- To evaluate whether patients with a low mGFR/eGFR ratio on days 1 and 3 are at higher risk of developing acute kidney injury (AKI) within the following 48-72 hours.

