## **7 Statistical analyses / methods**

### **7.1 General remarks**

The primary objective is to assess the safety and function of the FAST PV and mGFR Technology in hospitalized patients with heart failure. This is a phase II trial. No formal hypothesis test is performed to assess the primary objective. This is justified as follows: 1. Both function and safety cannot be uniquely assessed by one specific endpoint, but there exist several relevant endpoints and endpoint-related criteria which must be investigated in order to assess the global function and safety. 2. For reasons of feasibility, the studies sample size is limited to 50 patients which is an adequate number in the context of a phase II trial. However, this limited number does not allow to address a complex multiple testing problem with adequate power.

Therefore, all analyses including p values are purely descriptive. The aim is to generate new hypotheses to be tested in subsequent phase III trials.

For continuous variables descriptive statistics include mean, standard deviation, median, inter quartile range and range. For categorical variables descriptive statistics include absolute and relative frequencies.

Due to the low number of patients in one of the centers, no adjustment for center will be done in the analyses.

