### 7.7 Secondary analyses

#### 7.7.1 Efficacy

To evaluate how estimated PV (ePV) and estimated total blood volume (eTBV) assessments on days 1 and 3 (by Nadler's formula, Kaplan-Hakim formula) predict measured PV (mPV; as assessed by FAST methodology) and measured TBV (mTBV; calculated from mPV and measured hematocrit) at these time points, linear regression models with the measured values at a given day as dependent variable and the estimated version as independent variable will be generated. The models will be adjusted for BMI, weight, and height separately.

Further, Bland-Altman plots will be generated comparing the estimated and measured parameters separately for day 1 and day 3. The defined limits of agreement are  $\pm 500\text{ml}$  for TBV and  $\pm 300\text{ml}$  and for PV. The amount of values within 15% and within 30% of the measured values will also be determined. In addition, the diagnostic test accuracy including 95% confidence interval as proposed by Obuchowski (Obuchowski, 2005) will be calculated. The interpretation for a continuous reference standard is as follows: Of two randomly chosen patients, the diagnostic accuracy is the probability that the patient with the higher reference standard result has a higher diagnostic test result than the patient with the lower reference standard test result. In the case of the study, the measured PV and TBV will act as reference standard while the estimated versions serve the diagnostic test.

To evaluate how a clinical evaluation on days 1 and 3 predicts mPV and mTBV at these time points, linear regression models will be used.

Depending on the amount of available information and distribution, the following parameters will be considered for the analysis in the order of appearance: hematocrit (only PV), mean arterial blood pressure, BMI (only PV), weight, height (BMI, weight, height will be entered in 3 separate models), age, gender, NYHA stage, respiratory rate, edema grade, presence of pulmonary rales, jugular venous congestion. At least 10 observations will be needed per parameter that need to be estimated. Bland-Altman plots, frequencies within 15% and 30%, and diagnostic accuracy will be evaluated as stated before.

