### 7.7.2 Safety/Tolerability

#### **Adverse events**

AEs and SAEs will be regarded for safety analysis if they are treatment emergent, i.e. if they were not present prior to the first application of VFI or in case they were present and are worsening after the first application of VFI.

All AEs, whether or not they are considered to be related to treatment are reported.

They are listed by subject providing the following information:

- Age, sex, weight, BMI
- The adverse event (reported term by investigator, MedDRA preferred term, System Organ Class)
- Date of onset
- Duration of the adverse event
- Severity
- Seriousness (serious/non-serious)
- Action taken
- Outcome
- Causality assessment

The adverse events are displayed in summary tables as follows:

- A table of the preferred terms of all AEs will be presented including the number and percentage of subjects in whom at least one event with the respective preferred term (PT) occurred. The PTs will be grouped by MedDRA System Organ Class (SOC) and sorted by frequency.
- Additionally, the number and percentage of subjects in whom at least one event in the respective SOC occurred will be given.
- The tables above will be additionally divided into the defined severity categories grouped by relatedness of the event to VFI.

Every table will be produced for the following AE sets:

- All AEs
- AEs for which a relationship to formula intake was considered to be related by the investigator

Such AEs which were documented as SAEs will be reported in the same way as the AEs.

Every table will be produced for the following SAE sets:

- All SAEs
- SAEs for which a relationship to VFI cannot be ruled out
- All SAEs with outcome death

Additionally, all deaths during the study and deaths that resulted from a process that began during the study are listed by subject.

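### The primary count of related events omits those graded Cannot be evaluated, and the primary proportions carry no confidence interval

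*SAP*

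**What the plan says.** Protocol 10.8.1 grades causality on six levels: sure, probable, possible, unlikely, not related, and cannot be evaluated. The last is defined as "The causality cannot be determined". *Unlikely* covers events whose timing "makes a relationship improbable (but not impossible").

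SAP 7.6 defines the primary safety numerator: "Related AEs and SAEs include all events that are sure, probable and possible related". It does not mention *Cannot be evaluated*. Among its SAE tables, SAP 7.7.2 includes "SAEs for which a relationship to VFI cannot be ruled out". The matching AE table uses a third wording, based on what the investigator considered related.

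SAP 7.6 plans the primary proportions as frequencies. They are related AEs and SAEs, patients with stable FD003 on Day 1 and Day 3, and patients whose FD003 falls by more than 10% from 15 to 30 or from 30 to 60 minutes on each day. SAP 7.1 adds no interval: "For categorical variables descriptive statistics include absolute and relative frequencies". Of the decline percentage, SAP 1.1 says: "This percentage should be ideally close to 0". The protocol's Size Estimation says that "the sample size of 50 patients is sufficient to guarantee reasonable accuracy with respect to the main objectives of the trial". The intervals the SAP does plan are in 7.7.1, for a secondary quantity: "the diagnostic test accuracy including 95% confidence interval".

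**The concern.** In a single-arm trial, these proportions are the safety result and part of the function result. Two things are left open.

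First, an event whose cause nobody could judge is kept out of the related count, and no parallel count is planned that shows the effect. If 7.7.2 is read differently from 7.6, one report could give two numbers for what looks like the same quantity, related SAEs.

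Second, the plan claims accuracy for 50 patients and sets an informal target near zero, but it provides nothing by which a reader can judge either. A bare 0% would look as if it met the target whatever its uncertainty.

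**Working it through.** **1. Causality levels.** The six levels of protocol 10.8.1, set against the SAP rules:

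| Level | SAP 7.6 | SAP 7.7.2 SAEs, meant as 7.6 | SAP 7.7.2 SAEs, read literally |
|---|---|---|---|
| Sure | in | in | in |
| Probable | in | in | in |
| Possible | in | in | in |
| Unlikely | out | out | in |
| Not related | out | out | out |
| Cannot be evaluated | out | out | in |
| Levels counted | 3 of 6 | 3 of 6 | 5 of 6 |

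SAP 5.1 requires the relationship field to be complete. That does not settle the matter, because *Cannot be evaluated* is a valid entry and not a missing one.

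**2. Direction and size.** Let r be the number of patients with at least one event graded sure, probable or possible. Let c be the number with no such event but at least one graded *Cannot be evaluated*. With N patients, SAP 7.6 reports r/N and the inclusive count is (r + c)/N. The difference is c/N, which is never negative. At N = 50, each such patient adds 1/50 = 2 percentage points. The documents give no basis for estimating c. As an illustration for SAEs, r = 0 and c = 1 gives 0/50 under 7.6 and 1/50 under the literal reading of 7.7.2.

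**3. Precision.** The documents state no precision figure, so there is none to reproduce. The exact (Clopper-Pearson) 95% limits for x events in n patients are the 2.5% quantile of Beta(x, n − x + 1) and the 97.5% quantile of Beta(x + 1, n − x). With x = 0 the lower limit is 0 and the upper limit is 1 − 0.025^(1/n). For n = 50, that is 1 − 0.025^(1/50) = 0.0711.

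| Observed | Rate | Exact 95% interval |
|---|---|---|
| 0/50 | 0% | 0 to 7.1% |
| 1/50 | 2% | 0.1 to 10.6% |
| 2/50 | 4% | 0.5 to 13.7% |
| 3/50 | 6% | 1.3 to 16.5% |
| 0/45 (n assumed) | 0% | 0 to 7.9% |
| 0/40 (n assumed) | 0% | 0 to 8.8% |

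The stable-FD003 proportion mirrors this: 50 stable of 50 has a lower limit of 100 − 7.1 = 92.9%. The planned 50 is used as the Day 1 denominator. The values 45 and 40 are assumptions that show how Day 3 widens if some second doses are missed.

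**The case against.** The strongest reply is that nothing is lost. SAP 7.7.2 tabulates all AEs and all SAEs whatever their relationship, splits the tables by relatedness, and lists causality for each subject. A three-level rule also fits the protocol synopsis, which speaks of events related or possibly related to VFI. The data review meeting in SAP 6 can add to the analysis before it starts. Both documents call the analysis purely descriptive, and anyone can compute an exact interval from a count. Most of this stands, and it keeps the point small. It does not remove it: a confidence interval is itself descriptive and needs no test, and the SAP already plans one for a secondary quantity.

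A reader might go further than the documents allow in several ways.

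- *That the SAP declares unassessable events unrelated.* It does not say so; the level is left out of the list.
- *That the report will carry two conflicting SAE counts.* This follows only from the literal reading. If the 7.7.2 wording is shorthand for the 7.6 list, the counts agree. On the literal reading, the 7.7.2 table would itself already include the unassessable SAEs, along with the unlikely ones.
- *That SAP 7.5 expects missing second doses.* It says only that reasons will be listed.
- *That the SAP dropped an interval the protocol had planned for the adjudication answers.* The protocol's interval was for yes answers. SAP 7.7.1 replaced those questions with ones scored from 1 to 5, so the interval has no direct counterpart.
- *That 50 patients is too few.* Neither document sets a rate to be excluded, so there is no standard against which to call the number inadequate.

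**Conclusion.** The point holds as a minor one that should be corrected. *Cannot be evaluated* events are outside the primary related count by omission. The effect is c/N, in one direction only and of unknown size. The wording of 7.6 and 7.7.2 should be aligned, because two related-SAE counts are possible though not certain. The primary proportions lack any measure of precision, and at 50 patients even a result of zero is compatible with a true rate of up to 7.1%.

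This rests on three assumptions: that the safety frequencies are per patient (SAP 7.6 does not say so, although the 7.7.2 tables count subjects), that all 50 patients are in the full analysis set, and that all are evaluable for FD003 on Day 1. No figure in either document is contradicted, and no conclusion of the trial is shown to change.

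**What to change.** (a) State one definition of related, covering all six causality levels, and use it in SAP 7.6 and in the AE and SAE tables of 7.7.2. Either count *Cannot be evaluated* as related, or report a sensitivity count that includes it.

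(b) State that the related AE and SAE frequencies are per patient in the full analysis set. Report exact 95% intervals for these proportions, for the proportion with stable FD003 on Day 1 and Day 3, and for the proportions with an FD003 decline above 10% in each interval on each day. Use the actual denominators.

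(c) State the precision at 50 patients (0/50: 0 to 7.1%; 1/50: 0.1 to 10.6%; 2/50: 0.5 to 13.7%), and note that Day 3 will be wider if second doses are missed.

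The cost is a few sentences and some table columns, with no new data. The reported related rate may come out slightly less favourable.

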### 3.1.3.2 First-in-Human Study

A FIH study, representing the first human use of the VFI, was concluded in 2012. Data from the study indicated that the FAST PV and mGFR Technology is safe and well tolerated. In this study, 32 patients were enrolled with 8 patients (6 VFI + 2 placebo) assigned to 1 of 4 dose groups. The VFI agent consisted of a mixture of 2 different molecular weight carboxymethyl dextran molecules (5 kD [FD001] and 150 kD [FD003]) with different fluorescent dye molecules attached. Four increasing doses were administered through a bolus injection: Group 1, 5 mg/0.1 mL VFI; Group 2, 15 mg/0.3 mL VFI; Group 3, 75 mg/1.5 mL VFI; Group 4, 150 mg/3 mL VFI.

All 32 patients completed the study as planned and were included in the safety analysis. Overall 9 patients (28.1%) experienced 15 treatment-emergent adverse events (TEAEs) which were considered by the investigator to be reasonably related to VFI administration or study procedures. Most related TEAEs were observed after administration of 15 mg VFI (9 TEAEs reported by 3 patients). No related TEAEs were observed after the highest dose. Only 2 patients (both 15 mg VFI) reported 6 TEAEs (pruritus and gastrointestinal disorders) which were considered related to VFI administration. All other related TEAEs were judged to be related to the study procedures (mainly injection site pain and hematoma at the blood sampling site). All TEAEs were of mild to moderate intensity. There were no serious adverse events

(SAEs); no patient discontinued the study due to adverse events (AEs). Safety laboratory parameters, vital signs, and electrocardiogram (ECG) parameters showed no clinically relevant time- or treatment-related effects or differences between dose groups.

All patients who received VFI were included in the PK analysis. Geometric mean AUC and  $C_{max}$  of FD001 and FD003 increased dose-proportionally. FD001 had a median time at which the maximum concentration was observed ( $t_{max}$ ) of 0.25 hours for all doses; median  $t_{max}$  of FD003 was about 0.5 hours for the 2 lower doses and 2 hours for the 2 higher doses. FD001 was eliminated with a short elimination half-life ( $t_{1/2}$ ) of about 1.5 to 4 hours; mean  $t_{1/2}$  for FD003 was considerably longer ranging from 47 to 111 hours. Detailed PK data is available in the Investigator's Brochure for this study.

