Following administration of 75 mg VFI by IV bolus injection to adults with preserved kidney function and impaired kidney function, mean plasma FD003 concentrations exhibited little variability within study groups for samples collected from 0.25 to 504 hours. Plasma FD003 concentrations reached maximum concentrations within 1 hour in all study groups and decreased in a mono-exponential, first-order elimination manner with measureable concentrations observed in all patients at 504 hours. The observed half-life of FD003 ranged from 90 hours for healthy patients to 125 hours for patients with severely impaired kidney function ( $eGFR \geq 15$  and  $< 30$  mL/min/1.73 m^2) and were generally similar irrespective of renal function. Mean FD003 volume estimates indicated that FD003 appeared to occupy a volume space that corresponds with PV. Mean FD003 CL did not change with decreasing renal function. No significant differences were observed in FD003  $C_{max}$  ( $p = 0.0743$ ),  $t_{max}$  ( $p = 0.0600$ ),  $AUC_{last}$  ( $p = 0.8469$ ),  $AUC_{inf}$  ( $p = 0.8684$ ),  $t_{1/2,z}$  ( $p = 0.0508$ ),  $V_z$  ( $p = 0.2644$ ),  $V_{ss}$  ( $p = 0.3305$ ), CL ( $p = 0.5048$ ),  $C_{max}/Dose$  ( $p = 0.1652$ ), or  $AUC_{inf}/Dose$  ( $p = 0.5048$ ). A delay in the dispersion of the FD003 molecule initially after dosing resulting in a later than anticipated  $C_{max}$ . Complete PK data for the Phase 2a study is located in the Investigator's Brochure from this study.

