### **3.2.2 Rationale for Study Design**

This is an investigator-initiated, one-armed phase II clinical trial designed to evaluate the safety and functionality of the FAST PV and mGFR Technology in CHF patients.

Previous clinical studies have shown the FAST technology to be safe and functional in patients with chronic kidney disease (CKD) and in healthy subjects. The technology has not been studied in CHF patients. In previous clinical studies, the technology has been demonstrated to accurately measure PV and mGFR in patients with CKD and healthy patients when compared to other clinical techniques including, eGFR calculations, Iohexol clearance and Nadler's formula. Additionally, previous studies have shown that the concentration of the PV marker remains relatively constant during the first two hours after injection, given that this high-molecular weight marker is predicted to exclusively occupy the intravascular compartment and exhibit a long half-life.

In this study, the safety and functionality of the FAST Technology will be evaluated in CHF patients. The non-clinical and clinical history of the product provides confidence that the technology will be well tolerated and function correctly in the CHF population.

The blood samples are timed to maximize the information gathered during the study. In addition to measurements of PV and GFR, FAST will determine the technology's functionality by comparing the concentration of the PV marker at the 15, 30 and 60 minute time points. It is not believed that the plasma volume will change significantly within that time period and thus the concentration of the PV marker should remain relatively constant.

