## 4 Study objectives

### 4.1 Primary endpoints

Global aim is to assess the safety and function of the FAST PV and mGFR Technology in hospitalized patients with heart failure.

- Safety will be assessed by determination of the absolute and relative frequencies of AEs and SAEs related to VFI.
- Function of the FAST PV measurement will be assessed by determining the plasma stability of the FD003 high molecular weight marker over the 15, 30, and 60 minute blood draws and applying the following criteria:
  - The FAST PV measurement is considered as stable, if the mean plasma concentration of FD003 at 30 minutes is not more than 10% lower than the mean plasma concentration at 15 minutes AND if the mean plasma concentration at 60 minutes is not more than 10% lower than the mean plasma concentration at 30 minutes
  - We will determine the percentage of patients which show a decline in the plasma concentration of FD003 of more than 10% from 15min to 30min and separately from 30 min to 60min. This percentage should be ideally close to 0.

---

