### **Primary objectives:**

Global aim is to assess the safety and function of the FAST PV and mGFR Technology in hospitalized patients with heart failure.

- Safety will be assessed by determination of the absolute and relative frequencies of AEs and SAEs related to VFI.
- Function of the FAST PV measurement will be assessed by determining the plasma stability of the FD003 high molecular weight marker over the 15, 30, and 60 minute blood draws and applying the following criteria:
  - The FAST PV measurement is considered as stable, if the mean plasma concentration of FD003 at 30 minutes is not more than 10% lower than the mean plasma concentration at 15 minutes AND if the mean plasma concentration at 60 minutes is not more than 10% lower than the mean plasma concentration at 30 minutes
  - We will determine the percentage of patients which show a decline in the plasma concentration of FD003 of more than 10% from 15min to 30min and separately from 30 min to 60min. This percentage should be ideally close to 0.

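### The primary FD003 stability rule counts only falls, so it tests marker loss but cannot flag incomplete mixing

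*SAP*

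**What the plan says.** The function part of the primary objective is judged on FD003 at 15, 30 and 60 minutes. Under SAP 7.6 the first of two conditions for stability is met when the "mean plasma concentration of FD003 at 30 minutes is not more than 10% lower than the mean plasma concentration at 15 minutes". The second condition applies the same 10% limit to a fall between the 30- and 60-minute means, and both must hold. At patient level, SAP 7.6 counts "patients which show a decline in the plasma concentration of FD003 of more than 10% from 15 minutes to 30 minutes", and does the same for 30 to 60 minutes. Protocol 4.1 and section 14 carry the same rule; section 14 asks for the "percentage of patients which show a decline in the plasma concentration of FD003 of more than 10% from 15min to 30min". Neither document sets an upper limit.

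SAP 7.6 also displays the absolute and relative change over each interval, for Day 1 and Day 3 separately. This display has no threshold.

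The reason for the endpoint is in Protocol 3.2.2: plasma volume is not expected to change much in the window, so "the concentration of the PV marker should remain relatively constant".

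**The concern.** Constancy has two sides and the rule has one. PV is read from FD003 by dilution (Protocol 3.1.2), so a rise moves apparent PV as surely as a fall does.

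A rise after the first sample is also what the protocol's own summary points to. In the first-in-human study (Protocol 3.1.3.2) median FD003 tmax was about 0.5 hours at the two lower doses and "2 hours for the 2 higher doses". For Phase 2a (Protocol 3.1.3.3) the text reports "A delay in the dispersion of the FD003 molecule initially after dosing resulting in a later than anticipated" maximum concentration.

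At stake is the meaning of the word stable in the primary result. The trial could report stability in a population in which the technology has not been studied, while the 15- and 60-minute samples imply different plasma volumes. SAP 7.7.1 then uses mPV and mTBV as reference standards.

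**Working it through.** There is no planned figure to reproduce: the primary objective has no hypothesis test and N = 50 has no formal calculation.

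**Inputs from the documents.** Rule: pass if C30 ≥ 0.9 × C15 and C60 ≥ 0.9 × C30 (SAP 7.6). Dilution: apparent PV is proportional to dose / C (Protocol 3.1.2). FD003 half-life: 47–111 h (Protocol 3.1.3.2) and 90–125 h (Protocol 3.1.3.3).

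**Assumptions, not in the documents.** A 15-minute level at 90%, 85% or 80% of plateau. A between-patient SD of the 15–30 minute change of 5 percentage points, range 3–8.

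**1. The rule applied to example profiles.** Change in apparent PV from 15 to 60 minutes = C15/C60 − 1.

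| Change 15–30, 30–60 | C60/C15 | Apparent PV | Rule as written | ±10% per step | ±10% per step and over 15–60 |
|---|---|---|---|---|---|
| −11%, 0 | 0.89 | +12.4% | fails | fails | fails |
| −10%, −10% | 0.81 | +23.5% | passes | passes | fails |
| +10%, +10% | 1.21 | −17.4% | passes | passes | fails |
| +20%, 0 | 1.20 | −16.7% | passes | fails | fails |
| +25%, 0 (80/100/100) | 1.25 | −20.0% | passes | fails | fails |
| +100%, 0 | 2.00 | −50.0% | passes | fails | fails |

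Every rise passes the written rule, even a doubling. A limit per step alone still passes +10%/+10% and −10%/−10%, so a 15–60 minute limit is needed as well.

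**2. What the tested direction measures.** Elimination over 45 minutes = 1 − 2^(−0.75/t½), which is 1.1% at 47 h and 0.4% at 125 h. Normal elimination uses little of the 10% margin, so the rule tests leakage or dilution.

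**3. Size, as a scenario.** If the 15-minute level is a fraction f of plateau, apparent PV from that sample is too high by 1/f − 1:
- f = 0.90: 1/0.90 − 1 = 11.1%
- f = 0.85: 1/0.85 − 1 = 17.6%
- f = 0.80: 1/0.80 − 1 = 25.0%

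**4. Patient counts, as a scenario.** Suppose a mean 15–30 minute change of +15%, SD 5 points, normal. The share rising by more than 10% is Φ((15 − 10)/5) = Φ(1) = 0.841, and 50 × 0.841 ≈ 42 patients (37 at SD 8, 48 at SD 3). The decline count shows about 0 of 50 at each of these SDs.

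**5. Is a rise documented?** In the first-in-human study FD001 had a median tmax of 0.25 h at all doses, while FD003 peaked at about 0.5 h or 2 h. The median FD003 peak therefore came after 15 minutes at every dose from 5 to 150 mg, a range that brackets the 47 mg used here. That supports late mixing in kind. It does not give its size.

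**The case against.** The strongest reply has four parts.

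- **The display already shows rises.** Under SAP 7.1 continuous variables get mean, SD, median, interquartile range and range, and all analyses are descriptive. This is correct and lowers the severity. But SAP 7.6 still issues a defined verdict and a frequency of patients with stable FD003, and the display can alter neither.
- **One-sidedness has a logic.** The marker is meant to stay in the vessels with a long half-life, and a fall tests that. This stands, and is a reason to keep the existing rule as the marker-loss criterion. It does not make the rule a test of constancy.
- **The evidence for a rise is soft.** Protocol 3.2.2 says earlier studies found the concentration nearly constant for two hours. The 2-hour tmax comes from 75 and 150 mg, and the dispersion delay from 75 mg with 22.5 mg of FD003, against 12 mg here. Elimination from 15 minutes to 2 hours is only 1 − 2^(−1.75/t½) = 1.1% to 2.5% for half-lives of 111 to 47 h, so on so flat a curve small assay noise could place the peak late. All of this stands: a reader might infer that a material rise is expected at this dose, and the documents do not show that.
- **A rise need not be a failure.** True plasma volume contraction under diuresis raises the concentration, and the marker is then working. Protocol 3.1.1 claims that PV can be followed after one dose, and in Phase 2b FD003 tracked an induced volume change (Protocol 3.1.3.4). A reader might count every rise as a malfunction; the documents do not support that.

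**Conclusion.** The point holds as a should-fix, not a must-fix. The verdict and patient counts cannot register a rise of any size, while the stated rationale is constancy and late FD003 peaks are on record. This follows from the wording alone and needs no assumption.

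The size is conditional. The 11%, 18% and 25% rest on assumed plateau fractions and describe apparent PV from the 15-minute sample only. A reader might go further and infer that mPV is biased by that much, and so compare it with the SAP's ±10% status bands or its ±300 mL limit for PV. The documents do not support this. They do not say which samples yield mPV, and Protocol 3.1.1 refers only to an algorithm. The ±300 mL limit concerns agreement between estimated and measured PV, not drift within one test. No passage makes the use of mPV depend on the stable label.

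**What to change.** Keep the prespecified one-sided rule and the decline counts in SAP 7.6, labelled as the marker-loss criterion. Beside them, for Day 1 and Day 3, report:

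- (a) the number and percentage of patients with a rise of more than 10% from 15 to 30 minutes, and separately from 30 to 60 minutes;
- (b) a two-sided stability result: change within ±10% for 15–30, 30–60 and 15–60 minutes.

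Base any statement that the PV measurement is stable on both the marker-loss criterion and the two-sided result. State that rises need careful interpretation, because true contraction under diuresis also raises the concentration.

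The cost is some SAP text and a few table rows, with no new data. SAP section 3 says patients were enrolled, so the addition should be recorded in SAP section 8 as a change from the protocol before analysis. The reported stability rate may be lower even without drift: with mean change 0 and an assumed SD of 5 points, the 15–30 minute count goes from about 1.1 to 2.3 of 50 (5.3 to 10.6 at SD 8). One gap remains: a mixing rise and a marker loss that cancel within the window would still pass.
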